Group comparisons of changes in regional volumes and thicknesses will be analyzed using a series of one-way analyses of variance (ANOVAs). The Scheffé post hoc procedure will be used to examine differences between means; Pearson product-moment correlation coefficients evaluated the strength of relationships between of changes in regional volumes and thicknesses and cognitive measures. Receiver operator curve analyses will determine sensitivity and specificity of various MTA cut points for distinguishing between diagnostic groups. Hazard ratios (HRs) for specific predictors of MTA progression and regression will be calculated using a three-state Markov model in continuous time. The proportional intensity model will be used to analyze effects of covariates on HRs.

Exploratory Aim 2: Levels of AD-associated biomarkers in blood will be compared between placebo controls and Leukine® treatment groups. The identification of circulating biomarkers in AD is a relatively new field, with inconsistent biomarker level results reported as increased, decreased, or unchanged between studies [37]. These mixed results mean that standardized levels for AD-associated circulating biomarkers have yet to be established. Therefore, we will compare observed biomarker levels from our project to other published levels to explore whether any similarities are observed. This comparison, as well as our own results, will add to the AD-associated blood biomarker field of literature.

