Exploratory Aim 3: Amyloid PET scans will be performed using Pittsburgh Compound B (¹¹C-PiB), produced at UCD-AMC, which allows for amyloid-beta neuritic plaque density imaging, and will be used to test the hypothesis that Leukine® treatment of mild-to-moderate AD subjects reduces cerebral amyloid load. ¹¹C-PiB PET scans will be performed at screening and at the first follow-up visit (+/- 7 days depending upon scheduling availability). For quantification of the brain amyloid load, assessments will evaluate the screening ¹¹C-PiB scan before the baseline visit and another ¹¹C-PiB scan within +/- 7 days of the first follow-up visit after the end of treatment with Leukine® or placebo. The change from the screening ¹¹C-PiB scan's SUVR to follow-up SUVR will be analyzed by a contracted central reading facility (i.e., BioClinica, a specialty clinical trial services provider) using the subject's MRI to reduce white matter contamination, thereby increasing the SUVR signal change by eliminating counts in the region that do not change (white matter). The ¹¹C-PiB PET scans and accompanying MRI scans will be stripped of any personal identifying information, containing only the trial's randomized subject ID number and date. Data will be compared using parametric (SPM) and non-parametric (SnPM) statistical methods with family-wise error (FWE) and false discovery rate (FDR) corrections. Comparisons of SUVRs will be made between the first and second PET for each individual study participant. These differences will then be compared between placebo and treatments groups to

determine if Leukine[®] treatment changes amyloid load. The results of the ¹¹C-PiB PET quantitative analyses will not be used to make any treatment decisions.

Important Note: Full-dose data from the two sites will be combined and analyzed together for both safety and cognitive outcomes. Also, other statistical tests that may be utilized include: independent t-tests to examine differences between means; the Chi-square test to assess association between variables; and logistical regression to calculate the ratio of the odds of an event occurring in one group compared to another group.

Dosage:

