A summary of all study events are presented in Table 1. All interviews with subjects and potential subjects will be carried out in a private room. At the initial visit (screen), after informed consent is obtained, the MMSE is performed. If the subject qualifies on the MMSE entry criteria then vital signs are recorded, an ECG and a physical exam are performed, and 8 ml of blood is drawn for a CBC with differential, and a complete metabolic panel (CMP). A brain MRI will also be done during the screening period to exclude other causes of dementia and to assess for Medial Temporal Lobe Atrophy (MTA). Also, the first positron emission tomography (PET) scan, using ¹¹C-PiB, will be performed during the screening period to assess evidence of cerebral amyloid load. If the PET scan is performed on the same day as the MRI scan, the PET scan will be performed after the MRI scan. A qualitative read of the ¹¹C-PiB PET scan will be made to determine evidence of β -amyloid neuritic plaques. For women enrolled, who feel that there is a chance they may be pregnant, a pregnancy test will be administered. Clinically, if the patient cannot name their last menstrual period or is uncertain whether they are pregnant or not, a urine dipstick test is performed. The creatinine level from the CMP will also

be used to assess the Glomerular Filtration Rate (GFR). Also a list of all patient medications will be recorded. Patients will have to meet the inclusion/exclusion criteria (stability on AD medications for 2 months prior to screen and all other meds must be stable 30 days prior to screen). Particular caution will be paid to individuals taking Lithium or corticosteroids, but they will not be excluded from the study.

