Once the results are available, if the subject continues to meet entrance criteria they will return for their baseline Day 1 (randomization) visit. This visit takes place about 1 to 4 weeks after the screen visit. At this visit, vital signs are recorded, 33 ml of blood will be drawn for a CBC with differential, a complete metabolic panel (CMP), and for biomarker assays (for example, GM-CSF, IFN- γ , IL-1 β , IL-2, IL-6, IL-8, IL-10, IL-12p70, TNF- α , Eotaxin, IP-10, MCP-1, MCP-4, MIP-1 β , TARC, P-Tau, Total Tau, and A β species), and tests of cognition, such as the MMSE, ADAS-cog, the ADCS-ADL scale, Trails A, Trails B, CDR, and the Mohs Cancellation task, are administered. The test article will then be delivered by the unblinded pharmacist, administered subcutaneously by the (blinded) study nurse or clinician, and the subject then goes home.

Subsequent injections will also be administered at the clinic. About 4 ml of blood will be drawn for CBC plus differential approximately every three days during the treatment phase to monitor for leukocytosis (see safety monitoring plan), and an additional 4 ml of blood will be drawn for CMPs once every week of the treatment phase. Vital signs, injection site review, and adverse events will be recorded at each visit. At the last treatment visit approximately three weeks later, we will record vitals, perform a physical exam, review for adverse events, administer cognitive tests and draw 33 ml blood for a CBC with differential, a CMP, and biomarker assays. A brain MRI will be done for comparison with the initial screen MRI to assess for any changes in the Medial Temporal lobe and for any incidence of vasogenic edema and microhemorrhage.

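### The atrophy comparison is a one-way ANOVA of change that leaves out the screening value already collected; an ANCOVA would use it, for a gain that the documents do not size and that may be small

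*Combined protocol and SAP*

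**What the plan says.** **Atrophy (Data Analysis Plan, Tertiary Endpoint).** The arm comparison is given as: "Group comparisons of changes in regional volumes and thicknesses will be analyzed using a series of one-way analyses of variance (ANOVAs". A Scheffé post hoc step follows. Covariates are mentioned only for the Markov hazard ratios: "The proportional intensity model will be used to analyze effects of covariates on HRs".

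**Amyloid (Data Analysis Plan, Exploratory Aim 3).** "Comparisons of SUVRs will be made between the first and second PET for each individual study participant". Then: "These differences will then be compared between placebo and treatments groups". For the image analysis: "Data will be compared using parametric (SPM) and non-parametric (SnPM) statistical methods". No design matrix or covariate is stated.

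**Data available (Study Events).** "A brain MRI will also be done during the screening period". At the last treatment visit: "A brain MRI will be done for comparison with the initial screen MRI". The schedule table shows a third MRI at the first follow-up visit, and PET at screening and first follow-up.

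No ANCOVA appears in the documents. The Important Note that closes the analysis plan adds t tests, chi-square tests and logistic regression, none of them described as adjusting for a screening value.

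**The concern.** Subtracting the screening value fixes the slope of follow-up on screening at exactly 1. If the true slope is lower, part of the screening measurement error stays in the outcome. An arm that happens to start high will then tend to show a lower change, and the reverse. An ANCOVA estimates the slope instead and removes the chance imbalance. With about 20 people per arm such imbalance is common, and no stratification on an imaging value is described. At stake is the width of the intervals for Hypothesis 3 and, with qualifications, for Exploratory Hypothesis 3.

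**Working it through.** **The plan's own figure.** The only power statement is the table under Sample size considerations (alpha .20, power .60, t test). The exact noncentral t calculation gives 27/53, 10/20, 4/8 and 2/4 per group (one-tailed/two-tailed). The table has 27/53, 10/20, 4/8 and 3/4, so seven of the eight entries match and one differs by a single patient. The table concerns cognition. No SD, correlation, alpha or power is given for MRI or SUVR, so the comparison below is in standard errors.

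**Inputs.**
- Planned size: 20 per arm, N = 40 (Sample size considerations).
- PET, and the MRI at first follow-up, were added by one amendment when two cohorts of 10 remained (Trial History), so about N = 20 for those scans.
- The tracer changed from Amyvid to ¹¹C-PiB after the 30th participant (update on the current amendment). That leaves about N = 10 on PiB.
- Screening-to-follow-up correlation ρ: not in the documents. It is an assumption, shown as a range.

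**Formulas** (equal variances at both scans, SD = 1, one normally distributed covariate).
- Variance of change is proportional to 2(1 − ρ), and residual variance under ANCOVA to 1 − ρ². The ratio is (1 + ρ)/2.
- Estimating the slope multiplies this by (N − 3)/(N − 4): 37/36 = 1.028 at N = 40, 17/16 = 1.063 at N = 20, and 7/6 = 1.167 at N = 10.
- Break-even: ρ = 1 − 2/(N − 3), which is 0.946, 0.882 and 0.714 respectively.

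**Results** (SE of ANCOVA relative to the change-score comparison).

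| ρ | (1+ρ)/2 | × 37/36 | SE, N = 40 | Equivalent N (for 40) | SE, N = 20 | SE, N = 10 |
|---|---|---|---|---|---|---|
| 0.5 | 0.750 | 0.771 | −12.2% | 51.9 | −10.7% | −6.5% |
| 0.7 | 0.850 | 0.874 | −6.5% | 45.8 | −5.0% | −0.4% |
| 0.8 | 0.900 | 0.925 | −3.8% | 43.2 | −2.2% | +2.5% |
| 0.9 | 0.950 | 0.976 | −1.2% | 41.0 | +0.5% | +5.3% |
| 0.95 | 0.975 | 1.002 | +0.1% | 39.9 | +1.8% | +6.7% |
| 0.98 | 0.990 | 1.018 | +0.9% | 39.3 | +2.6% | +7.5% |

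A simulation of 60,000 trials at 20 per arm gave variance ratios of 0.771, 0.873, 0.976, 1.001 and 1.017 at ρ = 0.5, 0.7, 0.9, 0.95 and 0.98, in agreement with the third column.

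**Chance imbalance.** At 20 per arm the arm difference in a screening value has standard error √(2/20) = 0.32 SD, so a gap above 0.3 SD arises about 34% of the time. A gap of one standard error moves the change contrast by (1 − ρ) × 0.316/√(2(1 − ρ)) change-SDs: 0.16 at ρ = 0.5 and 0.10 at ρ = 0.8.

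**Scheffé.** The design has two arms, hence one contrast per region. With one contrast the Scheffé test is the ANOVA F test itself, so the step adds nothing.

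**The case against.** The strongest reply is that the gain may not exist. The screening and end-of-treatment MRIs come from the same person at most about 7 weeks apart (up to 4 weeks of screening plus about 3 weeks of treatment). Automated volumes over that interval could plausibly correlate above 0.946, where ANCOVA gains nothing at N = 40. Nothing in the documents rules this out, and it stands. The endpoint is also tertiary, in a pilot.

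Four stronger readings are tempting, and the documents do not support them.
- A reader might infer that the change-score test is biased, with regression to the mean passing for a drug effect. Allocation is randomised in permuted blocks, so the test is unbiased over randomisations and its error rate already allows for chance imbalance. The loss is one of precision.
- A reader might call the adjustment free. It needs no new data, but it costs one degree of freedom and, at N = 40, a 2.8% variance inflation.
- A reader might use alpha .20 and the power table to state the imaging power lost. Those figures were set for cognition.
- A reader might apply the same change directly to SUVR. Pooled screening SUVR would mix two tracers, so a single slope is not sound. In a PiB-only set of about 10, ANCOVA is less precise than the raw difference once ρ exceeds 0.714. The plan is also silent on SPM covariates and does not exclude them.

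What remains is that for atrophy the plan names a covariate-free method although the covariate is already scheduled. At N = 40 the possible loss from adjusting is about 1% of the SE, against a possible gain of about 12% at ρ = 0.5.

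**Conclusion.** The point holds for atrophy as a modest improvement in method. The planned ANOVA of change is valid, and an ANCOVA on the screening value would be more precise if ρ is below about 0.946 at N = 40. It would also adjust for chance screening imbalance. The size is conditional on ρ: from about 12% off the SE at ρ = 0.5 to about 1% at 0.9, and about 1% worse at 0.98. For the first follow-up MRI, where about 20 people may have the scan, break-even is 0.882.

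The figures assume equal variances at both scans. If these differ, the large-sample variance ratio is one minus the squared correlation of change with screening value, and at N = 40 that correlation must exceed 1/√37 = 0.16 in absolute value for ANCOVA to gain.

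For SUVR the case is weaker and depends on how tracer is handled. The trial's main conclusions on safety and cognition are not affected.

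**What to change.** **Atrophy.** In the Tertiary Endpoint paragraph, replace the one-way ANOVA of change with an ANCOVA of each regional change on arm and the screening value of that region. Fit it for the end-of-treatment scan and for the first follow-up scan, and report the adjusted arm difference with its 95% confidence interval. Delete the Scheffé step.

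**Amyloid.** In Exploratory Aim 3, adjust for screening SUVR only with tracer handled: either analyse within tracer, or put tracer and a tracer-specific slope in the model. Each slope then rests on its own tracer group, so the N = 20 column above is optimistic. If only about 10 PiB participants are analysed, keep the unadjusted difference.

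**Power.** Do not cite the cognition table or alpha .20 as the power for either imaging measure.

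**Cost.** Analysis-plan wording before unblinding and no new scans or visits. For atrophy the statistical cost is one degree of freedom and the slope-estimation inflation: 2.8% of variance at N = 40, or 6.3% if about 20 people have the follow-up scan.

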Before initiation of the current trial at the UCD site, fourteen participants enrolled in a preliminary study at USF. Of these 14 participants, 9 completed the entire study, including both follow-up visits; and the other 5 completed all treatment visits and at least one of the follow-up visits. Also, 3 of the 14 participants may have received the full Leukine® dose, but this number cannot be definite due to blinding of the study team at USF. Finally, the only AE's reported include injection site reactions seen in 6 patients (redness, raised, itching, bruising). No serious AE's were reported in these 14 participants.

The current trial (COMIRB #12-1273) was originally approved as a multi-site trial with recruitment efforts again, at USF, in Tampa, FL. USF's recruitment yielded 5 subjects who were enrolled into the current trial. Two of these subjects were screen failures and three completed the trial at USF. USF's last subject officially completed the trial on June 12th, 2015. However, due to USF's low recruitment, the decision was made to amend the protocol and close USF as a site. This amendment was approved by COMIRB on July 25th, 2016. Since the closure of the USF site, the research team at UCD has received all pertinent study data and study samples via secure HIPAA compliant practices.

[figure not shown]

Figure 4. Total Neuropsychological Performance in Hematopoietic Cell Transplant (HCT) Recipients Receiving GM-CSF+G-CSF versus G-CSF Only.

The GM-CSF+G-CSF group performed significantly better at 6 months post-HCT ($p=.04$), but there were no group differences at 12 months post-HCT ($p=.24$). The GM-CSF+G-CSF group improved significantly from baseline to 6 months post-HCT ($p=.01$) and from baseline to 12 months post-HCT ($p<.01$). The G-CSF group demonstrated no change from baseline to 6 months post-HCT ($p=.33$) but significant improvement from baseline to 12 months post-HCT ($p<.01$). Note: No patients received GM-CSF only. (GM-CSF: Granulocyte-Macrophage Colony-Stimulating Factor; G-CSF: Granulocyte Colony-Stimulating Factor)

EXPERIMENTAL DESIGN AND METHODS:

Recruitment:

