For recruitment at the UCD site, this pilot clinical trial of Leukine[®] in AD will utilize subjects with mild-to-moderate AD who are patients in the Memory and Dementia Clinic at the University of Colorado Hospital (UCH), of which the Co-Principal Investigator, [name] is the Clinical Director. Subjects will also be recruited from the Community. For recruitment at the USF site, this pilot clinical trial of GM-CSF utilized subjects with mild-to-moderate AD from the USF Byrd Alzheimer Institute Clinic patients and from the Tampa Bay Community. Recombinant human GM-CSF is commercially available from Sanofi/Genzyme Corporation as a recombinant molecule, i.e. Leukine[®]/Sargramostim, which is FDA-approved for use in elderly patients (> 55 years old) and has an outstanding safety record. To recruit from the community we will utilize study flyers posted at Anschutz Medical Campus, Clinicaltrials.gov and the UCD Clinical Trials Website. The consent process will emphasize the voluntary nature of the research study and the fact that declining participation will not alter clinical care. As help towards travel costs, patients will be informed that they will be receiving a \$75.00 gift card at the end of the three week treatment period even if they cannot or choose not to complete the study, and will receive a \$25.00 gift card after each of the follow up visits for a total of \$125.00.

Inclusion/exclusion criteria:

Subjects must be

1. age 55 to 85 years;
2. should have a mild-to-moderate AD diagnosis (MMSE 10-26 inclusive);
3. should have qualitative evidence of elevated cortical amyloid by PET imaging.
4. if on anti-dementia treatment should be on stable treatment for at least 2 months (i.e. cholinesterase inhibitor and/or Memantine or Axona);
5. stable on all other medications for at least 30 days prior to screen;
6. should be fluent in English;
7. should be physically able to participate by medical history, clinical exam and tests;
8. should have a study partner to accompany them to scheduled visits.

Exclusion criteria are

1. clinically relevant arrhythmias or uncontrolled hypertension;
2. a resting pulse less than 50;
3. active cancer other than non-melanoma skin cancers;
4. use of another investigatory drug within 2 months of screening;
5. significant stroke or head trauma by history or MRI;
6. Contraindication for having a MRI;
7. DSM-IV criteria for a current major psychiatric disorder;
8. sensitivity to yeast or yeast products;

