An automated rating system to grade the severity of atrophy in the entire medial temporal region (MTA) will be employed using the FreeSurfer software automated rating system of individual medial temporal structures, i.e., the HPC, ERC and perirhinal cortex (PRC), which are specific regions

of interest (ROI) in AD pathogenesis. We have shown that these individual and summed MTA scores distinguish AD and acute MCI subjects from normal elderly control subjects and predict progression from acute MCI to dementia/AD [46,47].

Brain MRI scans will be obtained on a 3.0-tesla MRI machine using proprietary three-dimensional magnetization-prepared rapid-acquisition gradient echo or the three-dimensional spoiled gradient recalled echo sequences; MRI scans will be acquired with isotropic resolution, and contiguous slices with thickness of 1.5 mm or less will be reconstructed. Multiple MRI scans without contrast are safe as they do not involve exposure to radiation. Some subjects may have difficulty lying motionless during the scan or may experience anxiety while in the scanner. This can be mitigated by administering a sedative prior to scanning.

Brain MRI scans at the UCD trial site will be performed in Building 400 on the Anschutz Medical Campus (AMC) at the University of Colorado and Denver VA Medical Center Brain Imaging Center, a component of the AMC's comprehensive Colorado Translational Research Imaging Center (C-TRIC). Scans may also be done in the University of Colorado Hospital Anschutz Outpatient Pavilion radiology department. Brain MRI scans at the USF trial site were performed at University Diagnostic Institute on the campus of the University of South Florida.

PET PROCEDURE – Pittsburgh Compound B (^{11}C -PiB):

The amyloid PET procedure will utilize the C-TRIC research PET scanner for human imaging studies. The Philips Gemini 64TF imaging system is located in Building 400 on the Anschutz Medical Campus at the University of Colorado and shares patient handling facilities with the Department of Psychiatry.

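### Tertiary MRI analysis: the ROC step needs diagnostic groups that the trial does not enrol, the Markov models are undefined and short of data, and the valid between-arm test has no designated measure and no error control across measures

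*Combined protocol and SAP*

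**What the plan says.** The Tertiary Endpoint part of the Data Analysis Plan lists five MRI analyses.

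- Between groups: "Group comparisons of changes in regional volumes and thicknesses will be analyzed using a series of one-way analyses of variance (ANOVAs"), followed by Scheffé post hoc comparisons of means.
- Pearson correlations of MRI change with cognitive measures.
- ROC curves: "Receiver operator curve analyses will determine sensitivity and specificity of various MTA cut points for distinguishing between diagnostic groups".
- Transition modelling: "Hazard ratios (HRs) for specific predictors of MTA progression and regression will be calculated using a three-state Markov model in continuous time".
- Covariates: "The proportional intensity model will be used to analyze effects of covariates on HRs".

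Three regions are named: hippocampus (HPC), entorhinal cortex (ERC) and perirhinal cortex (PRC). The same section and MRI Procedure also describe a grade for the whole medial temporal region (MTA).

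On population, the Inclusion/exclusion criteria require that a subject "should have a mild-to-moderate AD diagnosis (MMSE 10-26 inclusive"), now with a positive amyloid PET. Sample size considerations give two arms and 40 subjects in total. Hypothesis 3 is that treatment reverses MTA or stops its progression.

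**The concern.** Only the group comparison of change addresses Hypothesis 3, if the groups are read as the two arms. That reading is an inference, but the two-arm design and the hypothesis support it.

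The ROC step needs at least two diagnostic groups. The contrast that the protocol describes is in its account of previous work, where "these individual and summed MTA scores distinguish AD and acute MCI subjects from normal elderly control subjects". Neither MCI subjects nor normal controls are enrolled here, and treatment arms are not diagnostic groups.

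The Markov step needs defined states and enough observed transitions. The documents define none and give no transition rate.

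The ANOVA step leaves open which of several measures carries the conclusion. If that is settled after the data are seen, a chance difference in one region can be reported as an effect on atrophy.

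**Working it through.** **Stated figures.** The plan gives no sample size, alpha or power for MRI. Its only power figures are the t-test table in Sample size considerations (alpha .20, power .60, used for cognition). That table reproduces to within one subject per group. It does not bear on MRI, so 0.05 below is an assumption.

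**1. ROC.** Diagnoses required: two or more. Diagnoses enrolled: one. Sensitivity and specificity between diagnostic groups cannot be estimated from trial data.

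**2. Markov model: number of intervals.** MRI is done at screening, end of treatment and first follow-up (Study Events). Trial History shows that the follow-up MRI was added in the 2016 revision.

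- Ceiling, all 40 subjects with three scans: 40 × 2 = 80.
- If the 13 subjects in the April 2016 DSMB review had two scans: 13 × 1 + 27 × 2 = 67.
- If only the remaining two cohorts of 10 had three scans: 20 × 1 + 20 × 2 = 60.

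**Markov model: precision.** Assume that 5-20% of 60 intervals show a transition: E = 3 to 12 events. For a balanced binary predictor SE(log HR) = √(4/E); per SD of a continuous predictor it is about 1/√E. The 95% limits are the HR divided and multiplied by exp(1.96 × SE).

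| Events of one type | Binary predictor | Continuous, per SD |
|---|---|---|
| 12 | 3.1 | 1.8 |
| 6 | 5.0 | 2.2 |
| 3 | 9.6 | 3.1 |
| 1.5 | 24.5 | 5.0 |

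An even split of 3-12 events between progression and regression leaves 1.5-6 of each type, so the last row can apply, although a normal approximation means little there. These are best cases, because they treat transition times as known when the scans only bracket them.

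For a binary predictor, 80% power at two-sided 0.05 to detect HR 2 needs 4 × (1.960 + 0.842)² / (ln 2)² = 65.3, so 66 transitions of one type. That is 66/80 = 83% of even the maximum number of intervals.

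**3. ANOVA: what controls error.** The Bonferroni rule is stated for the neuropsychometry tests, and the family-wise and false-discovery corrections for PET. Scheffé is named for MRI, but with two arms its critical value is (2 − 1) × F(.95; 1, 38) = 4.098, and t(.975; 38)² = 2.024² = 4.098. It is the same test and controls nothing across regions or measures.

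**ANOVA: false positives.** At 0.05 per test and independence, the chance of at least one is 1 − .95^k:

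- k = 3 (one measure per region): 14.3%.
- k = 6 (volume and thickness in every region): 26.5%.

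Simulation at 20 per arm with correlation .8 between measures gives about 10% and 14%.

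**4. Cost and gain of the remedy.**

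- Detectable difference with 80% power at 20 per arm (noncentral t): d = 0.91 at 0.05 and 1.06 at 0.05/3 = 0.0167.
- Variance saved by ANCOVA over a change score: (1 − ρ)/2. At assumed scan-to-scan correlations of .98 and .9 this is 1% and 5%.

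**The case against.** The best counter-argument is about proportion. This is a tertiary endpoint in a 40-subject pilot with a safety primary, and strict multiplicity control is optional there. That limits the weight of the point. It does not make an ROC without groups or a Markov model without states usable.

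Several stronger readings are tempting, and the documents do not support them.

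- *The ANOVA is invalid.* It is not. A one-way ANOVA of change is a sound comparison of two randomised arms, and the gain from adding the screening value is small.
- *Six tests are planned.* The plan speaks of regional volumes and thicknesses without assigning both to every region. Six is what happens if both are tested everywhere.
- *No time point is given, so the count doubles.* Study Events ties medial temporal change to the end-of-treatment MRI, and Trial History says the follow-up MRI was added to look for ARIA.
- *Every hazard ratio would be uncertain by a factor of 3 to 10.* The plan speaks of predictors in general. That range applies to a balanced binary predictor at an assumed transition rate; a continuous predictor does better.
- *No ROC of any kind could be computed.* A mild-versus-moderate split could be, but it is not planned and would not test Hypothesis 3.
- *Pooling USF scans is an error.* The protocol notes that "Brain MRI scans at the USF trial site were performed at University Diagnostic Institute on the campus of the University of South Florida", and the Important Note on pooling covers safety and cognition without mentioning MRI. But of the five USF enrolments, "Two of these subjects were screen failures and three completed the trial at USF", and change is measured within subject. Silence here is not a mistake.

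It is also fair to say that the Markov sentence is the only one that separates regression from progression, which Hypothesis 3 mentions. A descriptive version could keep that distinction.

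**Conclusion.** The point stands in three parts of unequal firmness. The mismatch between the ROC step and the enrolled population, and the absence of Markov states, predictors and covariates, follow from the text alone. The shortage of transition data depends on an assumed 5-20% transition rate, but even the 80-interval ceiling leaves little room for informative hazard ratios. The ANOVA is the right comparison; its gap is that no key measure is chosen among regional volumes, thicknesses and the MTA grade, and no rule applies across them. The size of that gap, 10-14% for three tests and 14-27% for six, assumes 0.05 per test and correlations from .8 down to 0.

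The consequence is confined to how the MRI results can be read. It should be corrected, but it does not threaten the primary safety conclusion.

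**What to change.** Make these changes before unblinding.

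1. Delete the ROC and Scheffé sentences.
2. Delete the Markov and proportional-intensity sentences, or keep only a descriptive count by arm of subjects with progression and regression, using states defined in advance.
3. Replace the ANOVA sentence with: *Change from the screening MRI to the end-of-treatment MRI will be analysed by ANCOVA with treatment arm and the screening value. The treatment difference will be reported with a 95% CI. Change to the first follow-up MRI is supportive, and correlations with cognition are exploratory.*
4. Name the measure in advance, in one of two ways:
   - the single summed medial temporal (MTA) measure, giving one test; or
   - one stated measure per region, for example HPC volume, ERC thickness and PRC thickness, with Holm adjustment across the three at two-sided 0.05. This allocation should be declared as the analysts' choice, because the protocol does not make it.

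A sensitivity analysis without the three USF subjects is optional.

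The change is to wording only; no visits or scans are added. The ROC and hazard-ratio outputs are given up. Under the three-region option, 80% power at Holm's first step needs d of about 1.06 instead of 0.91; the single summed measure avoids that penalty. The covariate costs nothing to collect, and its precision gain is small, about 1-5% of variance under the assumed correlations.
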